7.2.2.3 Concomitant medications definitions and handling of missing or incomplete dates

Medications will be assigned as being prior to study treatment, concomitant with study treatment, or occurring in the Stabilisation Phase, based on the start and stop dates of the medication and the IMP dosing.

If the medication stop date is before the date of the first IMP dose, the medication will be assigned as being discontinued prior to study treatment. Otherwise, the medication will be assigned as being concomitant with study treatment unless the start date of the medication is after Visit 9 date, when it will then be classified as occurring in the post-treatment period.

Should the stop date for a medication be missing (not ongoing) or incomplete to the extent that it could be before, on or after the time of start of study treatment, then it will be assumed that the medication was stopped on or after the start of study treatment (i.e. reported as concomitant medication). Similarly, if it is not clear whether the medication start date was on or before, or after the Visit 9 date, then it will be assumed the medication was begun on or before the Visit 9 date (i.e. reported as a concomitant medication) (worst case approach).

For listings of medications, dates will be presented as they have been recorded (missing and partial dates will not be replaced).

7.2.2.4 Definition of treatment-emergent AEs and handling of missing or incomplete dates

A Treatment-Emergent AE (TEAE) is defined as an AE occurring or worsening on or after the first IMP dose. Events with an onset date at or after the patient has signed the ICF and prior to the first IMP dose will be classified as pre-treatment AEs.

In the event of an incomplete onset date, the event will be considered to be treatment-emergent unless the partial onset date information or complete or partial end date confirms onset or end prior to the first IMP dose date (worst case approach).

Analysis of TEAEs/SAEs will be performed separately for Acute Exacerbation Phase (from Study Day 1 until Day 14 included) and Stabilisation Phase (after Day 14 until Week 26), as well as overall (both study phases combined together). Events with an onset date after the date of Visit 9 (Day 14) will be classified as occurring during the Stabilisation Phase.

Should any onset date for a TEAE be incomplete then it will be assumed that the TEAE occurred during the Acute Exacerbation Phase, unless the partial onset date information confirms onset after

the Visit 9 date (worst case approach).

In case of partial onset date of COPD exacerbation reported in the ‘Acute Exacerbation COPD’ form of the eCRF, the onset of the event will be assumed as the first day of the month in the analysis of time to next COPD exacerbation.

For AEs listings, dates will be presented as they have been recorded (missing and partial dates will not be replaced).

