7.1.4.10 Time to next COPD exacerbation

The time to next COPD exacerbation (in days) is defined as:

(Date when first COPD exacerbation symptoms started – Date when current COPD exacerbation symptoms stopped),

where COPD exacerbations experienced during the study are recorded on the ‘Acute Exacerbation COPD’ form of the eCRF, i.e.:

- Start date of COPD exacerbation is the ‘date when symptoms started’ recorded on the form
- COPD exacerbation has an intensity recorded as ‘Mild’, ‘Moderate’ or ‘Severe’ on the form.

Table 4: Criteria for event/censored for assessment of Time to next COPD exacerbation

Situation	Date of event or Censoring	Time to next COPD exacerbation	Outcome
Subjects who had next COPD exacerbation	Date of next COPD exacerbation after entering in study	Time from when current COPD exacerbation symptoms stopped until Date of next COPD exacerbation after entering in study	Event
Subjects who never had COPD exacerbation in study period	Withdrawal or last contact date	Time from when current COPD exacerbation symptoms stopped until Date of withdrawal or last contact date	Censored
Subjects who died	Death date	Time from when current COPD exacerbation symptoms stopped until Date of death	Censored
Subjects who withdrew or were lost to follow-up during the study	Withdrawal or last contact date	Time from when current COPD exacerbation symptoms stopped until Date of withdrawal or last contact date	Censored

7.1.4.11 Time from hospitalisation admission until subject is medically ready for discharge (current COPD)

This time (in days) will be calculated as:

(Date subject is medically ready for discharge from hospital – Date of hospitalisation admission),

where ‘Date of hospitalisation admission’ and ‘Date subject is medically ready for discharge from hospital’ are recorded on the ‘Current COPD Exacerbation’ form of the eCRF.

Table 5: Criteria for event/censored for assessment of Time from hospitalisation admission until subject is medically ready for discharge (current COPD)

Situation	Date of event or Censoring	Time from hospitalisation admission until subject is medically ready for discharge	Outcome
Subjects who were medically ready for discharge from hospital	Date subject is medically ready for discharge	Time from hospitalisation admission until Time subject is medically ready for discharge	Event

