The following figures will be produced for the EXACT-PRO rolling average score:

- Mean EXACT-PRO rolling average score over time by treatment regimen (Acute Exacerbation Phase and Stabilisation Phase separately).
- Mean EXACT-PRO rolling average score change from baseline over time by treatment regimen (Acute Exacerbation Phase and Stabilisation Phase separately).

The same analysis as above will be performed for each of the 3 EXACT-PRO subscores.

8.6.3.11 Number of COPD-related exacerbations during the study derived from 'Acute Exacerbation COPD' form of the eCRF

COPD-related exacerbations during the study derived from the 'Acute Exacerbation COPD' form of the eCRF will be considered for this analysis.

Only COPD exacerbations with symptoms start date \geq first study treatment intake on the form will be included in the analysis. The ‘date when symptoms started’ recorded on the form will be defined as the start date of the COPD exacerbation.

The number and the percentage of patients with COPD exacerbations, the number of COPD exacerbations and the total follow-up time in years will be summarised by treatment regimen.

The rate of COPD exacerbations per patient per year will be calculated for each treatment regimen using a weighted approach (which consists of pooling all patients of a treatment regimen and dividing the total number of COPD exacerbations by the total follow-up time).

The number and the percentage of patients with COPD exacerbations, the number of COPD exacerbations and the COPD exacerbation rate per patient per year as above will also be presented by treatment regimen for each of the following types of COPD exacerbation:

- Mild COPD exacerbations (intensity recorded as ‘Mild’ on the form)
- Moderate COPD exacerbations (intensity recorded as ‘Moderate’ on the form)
- Severe COPD exacerbations (intensity recorded as ‘Severe’ on the form)
- Moderate/Severe COPD exacerbations (intensity recorded as ‘Moderate’ or ‘Severe’ on the form)
- COPD exacerbations resulting in death (i.e. COPD-related deaths; serious criteria ‘Results in death’ ticked on the form)
- COPD exacerbations requiring hospitalisation (i.e. serious criteria ‘Requires in-patient hospitalisation or prolongs existing hospitalisation’ ticked on the form).

Additionally (and more generally), the number (%) of patients with COPD exacerbations and the number of COPD exacerbations will be presented by treatment regimen for each of the following category:

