8.6.3.13 Time to next COPD exacerbation

8.6.3.13.1 Time to next COPD exacerbation derived from ‘Acute Exacerbation COPD’ form of the eCRF

See section 8.6.3.11 for the derivation of COPD-related exacerbations.

Time to next COPD exacerbation will be analysed using the Kaplan-Meier method. Patients without a COPD exacerbation or who are discontinued before having it will be considered as “censored” patients.

For the following study periods: [0-4) weeks, [4-8) weeks, [8-12) weeks, [12-16) weeks, [16-20) weeks and [20-26) weeks, the number of COPD exacerbation-free patients at the beginning of the period, the cumulative number of patients with COPD exacerbation at the end of the period and the probability of having experienced a COPD exacerbation at the end of the period with the associate two-sided 95% CIs will be presented by treatment regimen. The point estimates and the relative two-sided 95% CIs will be presented by treatment regimen for the 75th, 50th and 25th percentiles. A Kaplan-Meier plot will also be presented. Comparisons between treatment regimens will be

performed by means of the log-rank test. The p-values of the pairwise log-rank test comparisons will be displayed on the figure.

A similar analysis using the Kaplan-Meier method will be performed for:

- Time to next mild COPD exacerbation (intensity recorded as ‘Mild’ on the form)
- Time to next moderate COPD exacerbation (intensity recorded as ‘Moderate’ on the form)
- Time to next severe COPD exacerbation (intensity recorded as ‘Severe’ on the form)
- Time to next moderate/severe COPD exacerbation (intensity recorded as ‘Moderate’ or ‘Severe’ on the form).

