8.7.1 Adverse events

All AEs will be classified by SOC and PT according to the MedDRA Version 20.0 or higher.

AEs will be classified as pre-treatment AEs or TEAEs. Additionally, TEAEs will be classified as occurring during the Acute Exacerbation Phase (from Study Day 1 until Day 14 included) or occurring during the Stabilisation Phase (after Day 14 until Week 26).

Details for imputing missing or partial start dates of adverse events are described in Section 7.2.2.4.

Acute exacerbations of COPD reported in the ‘Acute Exacerbation COPD’ form of the eCRF will also be included in the analysis of AEs (tables and listings).

Notes:

- Two AEs with the same PT and classified in the same category (pre-treatment AE or TEAE) will be considered as two different events when calculating the “number of events” in the tables.
- Where a subject has the same AE, based on preferred terminology, reported multiple times in the same category (pre-treatment AE or TEAE), the subject will only be counted once at the preferred terminology level in AE frequency tables.
- Where a subject has multiple AEs within the same SOC in the same category (pre-treatment AE or TEAE), the subject will only be counted once at the SOC level in AE frequency tables.

Pre-treatment AEs and TEAEs will be presented separately. Pre-treatment AEs will be presented in the listings only.

An overall summary of AEs will be provided. The total number of events and number and proportion of subjects experiencing any AEs, TEAEs, TEAEs of special interest, AEs related to study medication, SAEs, SAEs related to study medication, severe AEs, AEs leading to permanent discontinuation of study treatment and AEs leading to death will be tabulated for each treatment regimen and overall. This overall summary of AEs will also be provided for TEAEs occurred during the Acute Exacerbation Phase and for TEAEs occurred during the Stabilisation Phase separately.

Additionally, TEAEs, TEAEs of special interest, related TEAEs, serious TEAEs, related SAEs, severe TEAEs, AEs leading to permanent discontinuation of study treatment and AEs leading to

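### In the time-to-next-exacerbation analysis, a relapse with an unknown onset day can be dated before the index symptoms stopped, because the first-of-month rule has no lower limit

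*SAP*

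**What the plan says.** Four SAP rules combine here. "Index" below means the current exacerbation that qualified the patient.

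- **Imputation (7.2.2.4).** For a partial onset date on the later-exacerbation form, "the onset of the event will be assumed as the first day of the month in the analysis of time to next COPD exacerbation". No floor at first dose or at index stop is given.
- **Time (7.1.4.10).** The endpoint is "Date when first COPD exacerbation symptoms started – Date when current COPD exacerbation symptoms stopped". Table 4 has rows for the event and three kinds of censoring, but nothing for a zero or negative time.
- **Filter (8.6.3.11).** The count section restricts events: "Only COPD exacerbations with symptoms start date" on or after "first study treatment intake on the form will be included in the analysis".
- **Link (8.6.3.13.1).** The time-to-next analysis takes over that derivation: "See section 8.6.3.11 for the derivation of COPD-related exacerbations".

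Three other places bear on the point. Criterion 4 in 7.1.4.13 shows that the form asks about exacerbations after the qualifying one subsided. For adverse events, 7.2.2.4 takes the opposite care with incomplete dates: "the event will be considered to be treatment-emergent unless the partial onset date information", or the end date, shows that it came before dosing. Finally, 8.7.1 says that exacerbations from the same "form of the eCRF will also be included in the analysis of AEs".

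**The concern.** An event on this form comes, by the form's own question, after the index episode. The first-of-month rule ignores that and can date the event before the episode it must follow. Kaplan-Meier and log-rank methods have no proper use for a negative time, and the SAP does not say what the program should do with one. The programmer would have to drop it, set it to zero or leave it, and these choices give different results.

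The failure is concentrated in short gaps. The protocol (9.2) names fewer relapses over time among the aims of treatment, so early relapses matter to this endpoint. The same relapse could also count as treatment-emergent in the safety tables and be missing, or carry an unusable time, in the efficacy analysis.

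**Working it through.** The documents give no figure for this rule, so there is none to reproduce. The check is date arithmetic with the SAP's own rules.

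**Worked cases.** Imputed time = 1st of the relapse month − index stop date.

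| First dose | Index stop | True relapse (day not recorded) | Imputed onset | Imputed time | True time |
|---|---|---|---|---|---|
| 5 Mar | 14 Mar | 27 Mar | 1 Mar, before first dose | −13 | +13 |
| 25 Mar | 6 Apr | 24 Apr | 1 Apr, after first dose | −5 | +18 |
| 20 Mar | 1 Apr | 20 Apr | 1 Apr | 0 | +19 |
| 5 Mar | 20 Mar | 10 Apr | 1 Apr | +12 | +21 |

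The last row shows the limit of the problem. Once the relapse crosses into a new month, the time is shortened but valid.

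**Share affected, by true gap.** Let g be the days from index stop to relapse, and let the stop fall evenly over a 365-day year. The imputed time is zero or negative exactly when stop and relapse share a calendar month. A month of m days has max(m − g, 0) such stop days, so for g up to 28 the share is (365 − 12g)/365. The zeros are stops on the 1st: 12/365 = 3.3% for g below 28, and 11/365 = 3.0% at g = 28.

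- g = 7: (365 − 84)/365 = 77.0%, of which 73.7% negative
- g = 14: (365 − 168)/365 = 54.0%, 50.7% negative
- g = 21: (365 − 252)/365 = 31.0%, 27.7% negative
- g = 28: (365 − 336)/365 = 7.9%, 4.9% negative
- g = 35 or more: 0%

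Enumerating all 365 first-dose dates gives the same values.

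**Averaged over an assumed spread of gaps.**

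- Uniform over 1–28 days: 1 − 12 × 14.5/365 = 52.3%.
- Uniform over 1–56 days: gaps 1–28 contribute 28 × 0.523 = 14.65. Gap 29 adds (4 × 1 + 7 × 2)/365 and gap 30 adds 7/365, together 0.07. The total of 14.72 divided by 56 is 26%.
- Uniform over 1–170 days: 14.72/170 = 9%.

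Without the zeros these are about 49%, 25% and 8%.

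**Imputed date before first dose.** With L the days from first dose to index stop, and L + g up to 27, this share is (365 − 12(L + g + 1))/365. The protocol (7.1) cites an exacerbation duration of 13 (6 to 24) days, used here only as a range for L. At g = 7 the share is 54.0% for L = 6, 31.0% for L = 13 and 0% for L = 24. All of these cases are already among the negative times. L changes how many could also meet the first-dose filter, not the total affected.

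**The case against.** The strongest objection concerns deletion. A reader might infer that such an event is removed and the patient censored as exacerbation-free. The documents do not establish this. The first-of-month rule is confined to the time-to-next analysis, while the filter sits in the count section and refers to the start date in connection with the form, which may well mean the recorded date. A recorded month that contains the first dose does not prove onset before dosing, and the adverse-event rule in the same SAP section would keep the event. Even if the event were filtered out, the patient would be censored only if no later exacerbation followed. This objection stands: deletion is one possible reading. It does not rescue the rule, because an event kept on its recorded date still gets a negative or zero time.

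A reader might also take the problem to affect early relapses in general, or about half of all partially dated ones. Neither follows. A shared calendar month is needed, and the 52% requires every relapse to fall within 28 days of index stop, which nothing in the documents supports. The protocol (7.1) cites about 32% of exacerbations within 8 weeks of the preceding one. Applied roughly to the 56-day result, 0.32 × 26% ≈ 8%, close to the 170-day figure.

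Two smaller points also stand. A zero time can be used in Kaplan-Meier estimation, so it is a lesser fault than a negative one. The SAP attaches its worst-case label to the adverse-event rules, not to this sentence, so no intent to be conservative should be read into it.

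**Conclusion.** The concern holds as a gap in a stated rule. With no lower limit, the rule gives an impossible negative time to a relapse with an unknown day that falls in the same calendar month as the index stop, and a zero time when that stop is on the 1st. Whether some of these events are also dropped depends on a filter date that the SAP leaves open.

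Per partially dated relapse, the share with a zero, negative or pre-dose onset is about 9% (uniform over 170 days), 26% (56 days) or 52% (28 days, an extreme case). These figures assume that index stops are spread evenly over the calendar, that the index stop date is known, and that only the day of onset is missing. The number of partial dates is not stated, so the effect on the log-rank tests cannot be sized.

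The reach is limited to the form-based secondary analyses of time to next exacerbation (overall and by intensity) and the adjudicated version in SAP 8.8.1, which follows the same approach. The EXACT-PRO version (8.6.3.13.2), which uses daily scores, and the FEV1 primary endpoint are untouched. The protocol (13.5.1) treats all analyses as exploratory. This is a minor point, worth correcting because it is cheap.

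**What to change.** Make three short additions to the SAP.

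1. In 7.2.2.4, for time to next exacerbation, set a missing onset day to the later of the 1st of the recorded month and the day after index symptoms stopped. Query the date if that floor falls outside the recorded month. In the worked cases this gives +1, +1 and +1 day, and leaves the valid +12 unchanged.
2. In 8.6.3.11, state that the first-dose filter uses the recorded date and excludes an event only if that date confirms onset before first dose. This matches the adverse-event rule already in 7.2.2.4.
3. In 7.1.4.10, state the time origin when the index stop date is missing or partial. Without a stop date the formula has no starting point, so falling back on first dose for the onset alone would not produce a time. The mid-month rule for partial stop dates in 7.2.2.2 is not stated to apply to this analysis.

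The floor takes the earliest admissible day and so shortens the true gap. A sensitivity analysis with a later admissible day would show whether that matters. The cost is a few sentences and a line or two of code, with no new data collection beyond date queries.

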7.2.2.5 Time since last documented COPD exacerbation

In order to calculate the time since last documented COPD exacerbation, the following rule will be applied for partial dates for last documented COPD exacerbation:

- if the day of the month is missing it is imputed to be the last day of the month.

The above will be flagged and described as a footnote in the appropriate listings.

7.2.3 Missing items in a questionnaire (CRQ) within a patient/visit

The method of data imputation to be used for CRQ is to substitute a person-specific estimate for any missing item, when the respondent answered at least 50% of the items in a scale or subscale. The estimate is the average score, across completed items in the same scale or subscale, for that respondent. Otherwise the average score will be set to missing for that patient/visit.

7.2.4 Handling of changes in study endpoints due to protocol amendments

The Appendix A summarises the key changes to each protocol amendment and which study endpoints are impacted by the protocol amendments.

Sensitivity and subgroup analyses will be performed on the study endpoints impacted by the protocol amendments, and are detailed throughout this SAP when applicable.

8 STATISTICAL METHODS

8.1 General statistical conventions

All statistical procedures will be completed using SAS version 9.4 or higher.

8.1.1 Populations for analysis

Demographic and baseline characteristics will be summarised in the Safety, ITT and PP populations, unless otherwise stated.

Analyses of the primary efficacy endpoint will be performed on the ITT population, and also on the PP population as a sensitivity analysis.

The secondary and exploratory efficacy endpoints will be analysed using the ITT and PP populations for this PoC and hypothesis-generating study.

[figure not shown]
The safety and tolerability variables will be analysed using the Safety population.

PK data will be analysed using the PK population.

For the populations to be considered in the subgroup analyses, see section 8.8.3 below.

8.1.2 Treatment groups

Statistics will be displayed for the following treatment groups:

8.1.3 Descriptive statistics

Continuous variables will be summarised using descriptive statistics including number of non-missing observations (n), arithmetic mean (Mean), median (Median), standard deviation (SD), minimum value (Min) and maximum value (Max). One additional decimal point for mean and median and 2 additional decimal points for SD will be used.

For categorical variables, summaries will include the number of non-missing observations (n) or the number of patients in the population (N) as applicable, the counts of subjects and percentages. Percentages will be rounded to one decimal place. The number of missing values will be presented as a separate category with no percentage, but only if any missing value is recorded in the data for that summary.

For efficacy and safety data, summary statistics will be presented at each visit when relevant. Changes from baseline will be summarised in a similar manner.

Data in summary tables will generally be presented on an Observed Cases (OC) basis.

8.1.4 Statistical significance

Unless otherwise stated, all statistical testing will be two-sided and conducted at the significance (alpha) level of 0.05. Two-sided 95% confidence intervals (CIs) will be provided when relevant. All three treatment regimens will be assessed by pairwise comparisons for efficacy data, and no adjustment for multiplicity will be made.

8.1.5 Definitions of Baseline

The efficacy/exploratory endpoints to be analysed separately during the Acute Exacerbation Phase and the Stabilisation Phase are the EXACT-PRO total score and subscores (and exacerbation parameters derived from EXACT-PRO), the change from baseline in CRQ over time and the change from baseline in mMRC dyspnoea scale over time.

For summary purposes, the baseline value for Acute Exacerbation Phase will be defined as the last non-missing value collected prior to the first dose of study medication, unless other specified. Moreover, for the efficacy/exploratory endpoints to be analysed separately during the Acute Exacerbation Phase (from Study Day 1 until Day 14) and the Stabilisation Phase (from Day 14 until Week 26), the baseline value for Stabilisation Phase will be defined as the value collected on Visit 9 (Day 14), unless other specified. For Stabilisation Phase, no value available prior to Visit 9 (Day 14) will be used for definition of baseline, as the patient might not yet be under stable condition for COPD prior to Day 14.

For EXACT-PRO, as there is no stable period during which EXACT-PRO scores are collected prior to administering the study drug, the definition of the Baseline EXACT-PRO from the user manual⁶ will not be used for Acute Exacerbation Phase. The score and subscores obtained on Day 1 of the EXACT-PRO observation period, which corresponds to Study Day 1, will be used as the baseline for Acute Exacerbation Phase. Moreover, the Baseline EXACT-PRO score (or subscores) for Stabilisation Phase will be defined as the mean EXACT score during the first 7 days of the Stabilisation Phase (Week 3; Days 15-21), with a minimum of 4 days of available data required to compute the baseline value. If 4 or more of the first 7 days of data are not available, the baseline EXACT-PRO score for Stabilisation Phase will not be calculated.

